# **10.2** Sample Size Determination

The primary aim of the study is to show that Eziclen®/Izinova® is not inferior to Klean-Prep® in the proportion of subjects with successful colon cleansing.

A non-inferiority margin of 15% has been selected for consistency with other studies in colon cleansing preparations.

Therefore assuming a success rate (excellent or good response) of 85% in both the Eziclen®/Izinova® and Klean-Prep® groups, a one-sided alpha of 0.025 and 90% power, 120 subjects are required per treatment group. Assuming a rate dropout/non-compliance to protocol of 4% based on previous studies and taking into account that subjects will be hospitalised for treatment administration, 125 subjects will be randomised in each treatment group, i.e. 250 subjects in total. Enrolment will be completed once 250 subjects have been randomised.

The primary endpoint of treatment success will be tested sequentially (hierarchical structure) with the first test being non-inferiority test based upon the treatment difference. A rejection of the null hypothesis will trigger superiority testing based upon the treatment difference.

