1.4.4 Planned sample size

The primary aim of the study is to show that Eziclen®/Izinova® is non-inferior to Klean-Prep® in the proportion of subjects with successful colon cleansing.

A non-inferiority margin of 15 % has been selected for consistency with other studies in colon cleansing preparations.

Therefore assuming a success rate (excellent or good response) of 85 % in both the Eziclen®/Izinova® and Klean-Prep® groups, a one-sided alpha of 0.025 and 90 % power, 120 subjects are required per treatment group. Assuming a rate dropout/non-compliance to protocol of 4 % based on previous studies and taking into account that subjects will be hospitalised for treatment administration, 125 subjects will be randomised in each treatment

22/62

group, i.e. 250 subjects in total. Enrolment will be completed once 250 subjects have been randomised.

The primary endpoint of treatment success will be tested sequentially (hierarchical structure) with the first test being non-inferiority test based upon the treatment difference. A rejection of the null hypothesis will trigger superiority testing based upon the treatment difference.

The two hypothesis tests are hierarchically structured so that the second test (superiority) will only be considered if the first test (non-inferiority) is rejected. The superiority test is powered to detect an absolute difference of 18 %. There is no alpha adjustment for the second test as a result of the hierarchical testing.

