class TRTP(ref='KLEAN-PREP') COUNTRYC(ref='Largest country'); model AVALC(EVENT='Yes') = TRTP COUNTRYC / link=identity; lsmeans TRTP / diff cl;

run;

No p-value will be displayed for the genmod model, since this would not be equivalent to the ones provided for the logistic procedure analysis.

In addition, the robustness of the results will be assessed in the mITT population by repeating the procedure logistic and estimating the 95 % CI of the treatment difference using the bootstrap method:

- The adjusted proportions will be estimated using the proc logistic model;
- 10'000 random samples will be generated using a proc surveyselect from the observed data with treatment and country as stratification and with seed=111;
- The adjusted proportions for each sample will be estimated using the same proc logistic model by replicate;
- The treatment differences will be derived for each sample;
- The 2.5 and 97.5 percentiles of the 10'000 estimated treatment differences will be considered for the 95 % CI of the treatment difference.

The following SAS code will be used:

```
proc logistic data=ADCC(where=(PARAM='Successful overall preparation' and
MITTFL='Y'));
    class TRTP(ref='KLEAN-PREP') COUNTRYC(ref='Largest country') /
    param=glm;
    model AVALC(EVENT='Yes') = TRTP COUNTRYC / link=logit firth;
    lsmeans TRTP / cl ilink;
    ods output lsmeans=lsm;
```

run;

proc transpose data=lsm out=_lsm;

var Mu; id TRTP;

run;

data diff;

```
set _lsm;
diff = EZICLEN - KLEAN-PREP;
```

run;

```
proc surveyselect data=ADCC(where=(PARAM='Successful overall preparation' and MITTFL='Y')) out=samples method=urs samprate=1 rep=10000 outhits seed=111; strata TRTP COUNTRYC;
```

run;

proc sort data=samples; by replicate; run;

proc logistic data=samples;

by replicate;

class replicate TRTP(ref='KLEAN-PREP') COUNTRYC(ref='Largest country') /
param=glm;
model AVALC(EVENT='Yes') = TRTP COUNTRYC / link=logit;
lsmeans TRTP / cl ilink;

ods output lsmeans=lsm_boot(keep=replicate TRTP Mu);

run;

```
proc sort data=lsm_boot; by replicate; run;
proc transpose data=lsm_boot out=_lsm_boot;
      var Mu;
      by replicate;
      id TRTP;
run;
data final;
      set _lsm_boot;
      diff = EZICLEN - KLEAN-PREP;
run;
proc sort data=final; by diff; run;
```

proc univariate data=final noprint;

var diff;

output out=ci95(rename=(Q2_5=Lower Q97_5=upper Q50=median)) pctlpre=Q pctlpts=2.5 50 97.5;

run;

No p-value will be displayed for this robustness analysis.

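### SAP 3.2.1.1: the bootstrap uses Firth for its point estimate but not in the 10,000 replicates, so a country of about 5 or fewer subjects per arm shifts this supportive interval toward zero

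*SAP*

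**What the plan says.** SAP 3.2.1.1 describes a bootstrap check of the primary result in the mITT population. Subjects are resampled within treatment by country, and the interval is taken from the 2.5 and 97.5 percentiles of the replicate differences. On the replicate model the text says: "The adjusted proportions for each sample will be estimated using the same proc logistic model by replicate".

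The code has two PROC LOGISTIC calls. The one for the point estimate reads "model AVALC(EVENT='Yes') = TRTP COUNTRYC / link=logit firth". The one run by replicate reads "model AVALC(EVENT='Yes') = TRTP COUNTRYC / link=logit" and ends there. Both obtain adjusted proportions from `lsmeans` with the inverse link.

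Three other places matter:

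- The SAP change log for version 4.0 records that the option (its name is misprinted there) was added to the bootstrap logistic for consistency with the primary model. Only one of the two calls carries it.
- SAP 3.2.1.1 justifies Firth in the primary interaction model by the risk of quasi-complete separation.
- The N.B. under the primary code removes both the interaction term and Firth when the interaction is not significant.

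**The concern.** Code, text and change log disagree about the replicate model, and the code is what will be run. The omission is more than cosmetic because resampling inside small treatment-by-country cells readily produces a country with no failures in either arm. That is the separation Firth is meant to handle. Without the penalty, such a replicate returns a difference close to zero whatever the data in the other countries show. The percentile limits can then describe a different estimator from the one reported beside them, and a robustness check can appear reassuring when it should not.

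**Working it through.** **Inputs (SAP 1.4.4, Protocol 10.2).** The plan works from "assuming a success rate (excellent or good response) of 85 % in both the" arms; "A non-inferiority margin of 15 % has been selected"; "a one-sided alpha of 0.025 and 90 % power, 120 subjects are required per treatment group". It adds 4% for dropout, and "125 subjects will be randomised in each treatment group, i.e. 250 subjects in total". Allocation is 1:1, stratified by country (Protocol 3.3), in around 25 centres. The number and size of countries are not stated and are assumed below.

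**Plan's own figure.** n = 2 × 0.85 × 0.15 × (1.960 + 1.282)² / 0.15² = 0.255 × 10.51 / 0.0225 = 119.1, so 120 per arm; 120 / 0.96 = 125. Reproduced.

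**Mechanism.** For arm t and K countries, the adjusted proportion is p_t = 1 / (1 + exp(-(a + b_t + (1/K) Σ c_k))), with every country weighted equally on the logit scale. If all resampled subjects in country k succeed, the maximum-likelihood c_k runs off upwards and lifts both arms. As an illustration, start from 85% and 70% (logits 1.735 and 0.847). With K = 5 and one coefficient inflated by 15 (an assumed value), each logit rises by 15/5 = 3, giving 99.1% and 97.9%. A difference of -15 points becomes -1.2.

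**How often a replicate is separated.** For a country with m per arm, the chance that all its resampled subjects succeed is the product over arms of E[(X/m)^m], with X binomial(m, p). For m = 5 this expectation is 0.583 at p = 0.85 and 0.311 at p = 0.70.

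- Both arms at 85%: 0.583² = 34% of replicates.
- 85% v 70%: 0.583 × 0.311 = 18%. Adding a country of 10 per arm (3.8% of replicates in the four-country row below) gives 1 - 0.818 × 0.962 = 21%, which matches the simulated 21.0% for 50/35/20/10/5.

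**Simulation.** 120 per arm; true rates 85% (Klean-Prep) v 70% (Eziclen/Izinova) in every country, so the true difference is exactly -15 points; 1,500 trials × 1,000 resamples. Entries are the percentage of trials with a lower limit above -15% (nominal 2.5%).

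| Assumed country sizes per arm | Replicates separated | Bootstrap as coded | Bootstrap, Firth in replicates | Primary without Firth |
|---|---|---|---|---|
| 40/40/40 | 0.0% | 2.3% | 2.9% | 2.3% |
| 60/40/20 | 0.2% | 2.7% | 2.9% | 2.7% |
| 24 × 5 | 0.3% | 2.8% | 3.1% | 2.7% |
| 50/40/20/10 | 3.8% | 4.0% | 3.3% | 3.5% |
| 50/35/20/10/5 | 21.0% | 10.7% | 3.2% | 10.2% |
| 60/35/17/5/3 | 46.3% | 27.9% | 4.0% | 27.7% |
| 45/30/20/12/7/4/2 | 66.0% | 45.7% | 4.5% | 46.7% |

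Monte Carlo standard errors: √(0.025 × 0.975 / 1500) = 0.4 points near nominal, and √(0.107 × 0.893 / 1500) = 0.8 points at 10.7%. In the last three rows the coded version passed where Firth failed in 7.5%, 23.9% and 41.2% of trials, and never the reverse.

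Further simulation runs with other splits agree in direction. As coded v Firth, 60/30/15/10/5 gave 9.0% v 2.8% in one run and 13% v 6% in another; 80/20/10/6/4 gave 21% v 6% and 23% v 7%. There was no meaningful difference for 50/40/30.

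At the planned 85% in both arms with 50/35/20/10/5, the mean interval is (-6.5%, 6.5%) as coded and (-8.5%, 8.6%) with Firth. The pass rates are 93.1% and 91.3%.

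**Worked data set.** Klean-Prep successes 42/50, 30/35, 17/20, 8/10, 5/5 (102/120 = 85.0%); Eziclen/Izinova 33/50, 24/35, 14/20, 7/10, 5/5 (83/120 = 69.2%). The Firth point estimate is -13.0%. The interval as coded is (-1.9%, -0.3%), or (-8.2%, -1.5%) if the likelihood stops after 8 iterations. Either interval excludes the reported estimate. With Firth it is (-21.3%, -4.5%).

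**The case against.** The strongest reply is that the unpenalised replicates match the primary model. When the interaction is not significant, the N.B. removes Firth there too, so the odd one out is the bootstrap's Firth point estimate. That stands. In the three small-country rows the primary itself passes in 10.2%, 27.7% and 46.7% of trials, almost the same as the coded bootstrap. A reader might infer that the missing option adds error beyond the primary's. The documents and figures do not support that: the bootstrap repeats the primary's error. The two bootstrap calls nevertheless still contradict each other and the text.

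A reader might also infer that the omission inflates the trial's false-positive rate. It does not. Non-inferiority is decided by the primary interval (SAP 3.1.5 and 3.2.1.1), and the bootstrap carries no p-value. The SAP also specifies an identity-link model, which has no diverging logit, and a per-protocol repeat. SAP 4.3 requires log warnings to be checked, which may reveal separated replicates.

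Nor is the bootstrap biased whatever the country sizes. It takes a very small country, and the documents do not say there is one. It is plausible: 250 subjects in about 25 centres is 10 per centre, or 5 per arm, so a country with one average centre would qualify. SAP 3.2.12 gives no rule for pooling small countries.

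**Conclusion.** The inconsistency is certain: the replicate code departs from the SAP's text and change log. Its effect is conditional. With a smallest country of about 5 or fewer per arm, the coded bootstrap clears the margin at a true -15 points in roughly 10 to 25% of trials, against about 3 to 7% with Firth; the most fragmented split tried reached 45.7%. At 10 per arm the effect is slight (4.0% v 3.3%), and at 20 or more it is negligible.

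Confidence is high in the mismatch and in the direction, and lower in the percentages. Those rest on assumed country sizes, equal success rates across countries, and an approximation to how SAS stops iterating under separation. Stopping at 8 iterations lowers 45.7% to 40.3% and leaves the direction unchanged. The point concerns a supportive analysis. It matters mainly because the check could not expose the same weakness in the primary main-effects model.

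**What to change.** 1. Add `firth` to the replicate PROC LOGISTIC, so that code, text and change log agree. This costs one word and a somewhat longer run.
2. Report the number of replicates in which a country is fully successful, so that a reader can judge the interval.
3. Keep Firth in the primary main-effects model when the interaction is dropped, so that the bootstrap checks the estimator it is meant to check. This is more than a coding correction: it changes the prespecified primary model and the N.B. in SAP 3.2.1.1, and so needs a documented SAP change before unblinding. If only step 1 is taken, the bootstrap will check an estimator that the primary does not use whenever the interaction is not significant.

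Firth removes most of the excess but not all of it where countries are tiny (up to 4.5% in the main simulation and 7% in the others, against 2.5%).

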3.2.1.2 Secondary efficacy analyses

Analysis of secondary efficacy endpoints will be performed on the ITT population and could be duplicated on mITT if there is a difference of more than 10% of subjects between ITT and mITT.

3.2.1.2.1 Colon cleansing score

The colon cleansing scores will be assessed by the 4-point scale (see Table 1) and will be presented by treatment group using descriptive summary statistics (mean, SD, median, quartiles and ranges) and using a two-way analysis of variance (ANOVA) including treatment and country as well as the interaction between treatment and country, if it is significant (i.e. p < 0.10), as covariates using the following SAS code:

proc mixed data=ADCC(where=(PARAM='Cleansing score' and ITTFL='Y')); class TRTP COUNTRYC; model AVAL = TRTP COUNTRYC TRTP*COUNTRYC; lsmeans TRTP / diff cl;

run;

The adjusted mean scores, the adjusted treatment difference with their 95 % CI and the p-value of difference will be summarised.

In addition, this analysis will also be produced per country so that mean scores and the estimated treatment differences will also be provided per country using the following SAS code.

```
proc mixed data=ADCC(where=(PARAM='Cleansing score' and ITTFL='Y'));
    class TRTP COUNTRYC;
    model AVAL = TRTP COUNTRYC TRTP*COUNTRYC;
    lsmeans TRTP*COUNTRYC / diff cl;
```

run;

3.2.1.2.2 Overall and segmental cleansing scores assessed by BBPS

The overall (LC + TC + RC) and segmental (LC, TC, RC) cleansing scores will be assessed by BBPS (see Table 3) and will be presented by treatment group using descriptive summary statistics (mean, SD, median, quartiles and ranges) and using a two-way analysis of variance (ANOVA) including treatment and country as well as the interaction between treatment and country, if it is significant (i.e. p < 0.10), as covariates using the following SAS code:

proc mixed data=ADCC(where=(PARAM='BBPS - Global Score'/'BBPS - Left colon score'/'BBPS - Transverse colon score'/'BBPS - Right colon score' and ITTFL='Y')); class TRTP COUNTRYC; model AVAL = TRTP COUNTRYC TRTP*COUNTRYC;

```
lsmeans TRTP / diff cl;
```

run;

30/62

The adjusted mean scores, the adjusted treatment differences with their 95 % CI and the p-value of difference will be summarised.

In addition, this analysis will also be produced per country so that mean scores and the estimated treatment differences will also be provided per country using the following SAS code.

proc mixed data=ADCC(where=(PARAM='BBPS - Global Score'/'BBPS - Left colon score'/'BBPS - Transverse colon score'/'BBPS - Right colon score' and ITTFL='Y')); class TRTP COUNTRYC; model AVAL = TRTP COUNTRYC TRTP*COUNTRYC; lsmeans TRTP*COUNTRYC / diff cl;

run;

The proportion of subjects with successful overall preparation, assessed by the total score of the BBPS, will also be presented. Successful overall preparation will be defined based on a global BBPS score ≥ 6 for the sum of the 3 segments (right, transverse and left colon) and will be presented by treatment group using frequency count with two-sided 95 % CI and analysed using Cochran-Mantel-Hænszel (CMH) chi-square for the proportions adjusting for country effect. The general association statistic will be used to assess the test significance.

The SAS Freq procedure will be used as follows:

```
proc freq data= ADCC(where=(PARAM='Successful overall preparation BBPS' and ITTFL='Y'));
```

table COUNTRYC*TRTP*AVALC / CMH;

run;

The difference of proportions with the 95 % CI and p-value will be summarised.

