**PAGE 29/103** 

Score	Grade	Description
4	Excellent	No more than small bits of adherent faeces/fluid
3	Good	Small amounts of faeces or fluid not interfering with examination
2	Fair	Enough faeces or fluid to prevent a completely reliable examination
1	Poor	Large amounts of faecal residue, additional cleansing required

Only perfect preparations graded as excellent (4) or good (3), which allow full, reliable examination of the mucosa, will be considered as successful.

Primary efficacy will be assessed on the basis of preparation success or failure.

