1.4.2 Subjects assessments

1.4.2.1 Efficacy assessments

Blinded overall assessment of preparation efficacy will be determined by the colonoscopist upon completion of the examination, based on a 4-point scale. The colonoscopist will score the quality of the bowel preparation using the following Cleansing Score (Table 1).

Score	Grade	Description
4	Excellent	No more than small bits of adherent faeces/fluid
3	Good	Small amounts of faeces or fluid not interfering with examination
2	Fair	Enough faeces or fluid to prevent a completely reliable examination
1	Poor	Large amounts of faecal residue, additional cleansing required

Table 1Cleansing Score

The primary efficacy will be assessed on the basis of preparation success or failure. The primary efficacy variable is the proportion of subjects with a successful overall preparation.

Only perfect preparations graded as excellent (4) or good (3), which allow full, reliable examination of the mucosa, will be considered as successful.

The secondary efficacy endpoints are summarised below (Table 2):

Endpoint	Timepoint	Evaluation
Colon cleansing	V2 (Colonoscopy)	Cleansing Score assessed on 4 levels (4-point scale, see Table 1).
Overall and segmental cleansing assessed by Boston Bowel Preparation Scale (BBPS)	V2 (Colonoscopy)	BBPS (see Table 3) Overall score [1]. Segmental scores (left colon (LC), transverse colon (TC), right colon (RC)).
Time to clear effluent (hours)	V1 (Treatment)	Time between first intake of prescription and first clear watery stool.
Complete procedure	V2 (Colonoscopy)	Number (%) of complete procedures defined as procedures that reached the caecum.
Time to caecal intubation (minutes)	V2 (Colonoscopy)	Time between the colonoscope introduction and the time to reach caecum.
Duration of examination (minutes)	V2 (Colonoscopy)	Time between the caecum is reached and the withdrawal of the colonoscope.
Need for rescue treatment because of inadequate preparation intake.	V2 (before colonoscopy)	Number (%) of procedures that need a rescue treatment (saline enema).
Treatment acceptability	V1 (Treatment)	Level of acceptability of treatment assessed using a 5- point Treatment Acceptability Questionnaire (see Table 4).
Need for nasogastric tube	V1 (Treatment)	Number (%) of subjects who need a nasogastric tube to complete preparation.
Treatment compliance	V1 (Treatment)	Percentage of volume of fluid taken relative to the planned volume of fluid to be taken

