Time between the last intake of fluids and the start of colonoscopy procedure (hours)	V1 (Treatment) and V2 (Colonoscopy)	Time between the end of treatment administration and the start of colonoscopy.

Table 2 Secondary Endpoints and Evaluation	ions
----------------------------------------------------	------

The overall and segmental cleansing as assessed by BBPS [1] is presented in Table 3.

 Table 3
 Boston Bowel Preparation Scale

Score per segment	BBPS definition
0	Unprepared colon segment with mucosa not seen due to solid stool that cannot be cleared
1	Portion of mucosa of the colon segment seen, but other areas of the colon segment not well seen due to staining, residual stool and/or opaque liquid.
2	Minor amount of residual staining, small fragments of stool and/or opaque liquid, but mucosa of colon segment seen well.
3	Entire mucosa of colon segment seen well with no residual staining, small fragments of stool and/or opaque liquid

Scores for the right colon (RC), transverse colon (TC) and left colon (LC) will be collected. Scores per segment will be summed to provide overall cleansing score.

The Treatment Acceptability Questionnaire will be completed by the caregiver or subject after the subject ends the intake of preparation. Caregivers will be asked to rate subject acceptability using the following categories (Table 4).

Very badly accepted/unacceptable	Subject showed great displeasure, compromising use of formulation
Badly but accepted	Subject showed displeasure with dosing but could be coaxed to take complete dose
Neither good nor bad	Subject showed no apparent displeasure and with little effort was coaxed to take complete dose
Well accepted	Subject appeared to enjoy the formulation and with little coaxing ingested complete dose
Very well accepted	Subject appeared eager and ingested complete dose without special coaxing

Table 4 Treatment Acceptability Questionnaire Categories

The compliance will be assessed from the treatment questionnaire which will be completed by the caregiver or subject after the subject ends the intake of preparation. The subject/caregiver will provide information about treatment preparation, residual volumes of preparation (volumes not taken by the subject) and start and stop times of intake. For the Eziclen®/Izinova® treatment only, information about the residual volume of water will be reported.

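### The BBPS success rule in the SAP rests on the total score alone, so a colon with one segment not seen, or not well seen, can be counted as a success

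*SAP*

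**What the plan says.** SAP 1.4.2.1 scores the right, transverse and left colon from 0 to 3 each and forms the overall score as a plain sum: "Scores per segment will be summed to provide overall cleansing score". Table 3 in that section gives the meaning of each score:

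- 0: "Unprepared colon segment with mucosa not seen due to solid stool that cannot be cleared".
- 1: part of the segment is seen, with "other areas of the colon segment not well seen due to staining" or other residue.
- 2: minor residue, described as "small fragments of stool and/or opaque liquid, but mucosa of colon segment seen well".
- 3: the whole segment is well seen, with no residue.

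SAP 3.2.1.2.2 then builds a responder variable from the sum: "The proportion of subjects with successful overall preparation, assessed by the total score of the BBPS, will also be presented". The cut-off is: "Successful overall preparation will be defined based on a global BBPS score ≥ 6 for the sum of the 3 segments". The arms are compared with a country-adjusted CMH test, and a difference in proportions is reported with its 95% CI and p-value.

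No per-segment minimum appears anywhere else. Item (3) of SAP Appendix 1 derives success for the 4-point Cleansing Score only. Protocol 7.2 and 7.3.2.1 describe the BBPS overall and segmental scores but set no success cut-off, so the SAP sentence is the only definition. SAP 3.1.5 makes all testing of secondary endpoints descriptive.

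**The concern.** A sum lets two clean segments make up for one that could not be examined. With left 3, transverse 3 and right 0, the total is 6 and the subject is a BBPS success, although Table 3 says that the right-colon mucosa was not seen at all. A reader of the results table would not expect that from the word success.

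The rule is also looser than the idea of success on the 4-point scale, where Protocol 3.2.1 counts only preparations "which allow full, reliable examination of the mucosa, will be considered as successful". The two responder variables have almost the same name in the SAP code, so they are likely to be read side by side.

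At stake is what one secondary responder rate means. Overall and segmental cleansing is a stated secondary objective, and this is the only BBPS responder analysis that the SAP text describes.

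**Working it through.** **Inputs.** Three segments, each scored 0, 1, 2 or 3, summed without weights (SAP 1.4.2.1). Success is a total of 6 or more (SAP 3.2.1.2.2). Mucosa is well seen only at 2 or 3 (SAP Table 3). The documents give no expected BBPS success rate, so there is no planned figure to reproduce.

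**Step 1: patterns that pass.** There are 4 × 4 × 4 = 64 ordered patterns. Those reaching 6 are:

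| Total | All segments 2 or more | One segment below 2 | Patterns |
|---|---|---|---|
| 6 | 2-2-2 (1) | 1-2-3 (6 orderings), 0-3-3 (3 orderings) | 10 |
| 7 | 2-2-3 (3) | 1-3-3 (3) | 6 |
| 8 | 2-3-3 (3) | none | 3 |
| 9 | 3-3-3 (1) | none | 1 |
| Sum | 8 | 12 | 20 |

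Of the 12, 3 contain a 0 and 6 + 3 = 9 contain a 1.

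**Step 2: limits of the problem.** A segment at 0 allows a total of at most 0 + 3 + 3 = 6, and a segment at 1 at most 1 + 3 + 3 = 7. Totals of 8 and 9 therefore cannot conceal a segment below 2. Two segments below 2 give at most 1 + 1 + 3 = 5, so a passing colon never has more than one such segment.

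**Step 3: patterns with a poor segment that fail.** Patterns with at least one segment below 2 number 64 − 8 = 56. Of these, 12 pass and 56 − 12 = 44 fail.

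**Step 4: the stricter rule.** If every segment is 2 or more, the total is at least 2 + 2 + 2 = 6. The stricter rule is therefore nested in the SAP rule, its success rate can only be equal or lower, and the number of qualifying patterns falls from 20 to 8.

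**Step 5: effect on the arm difference.** Let p be an arm's success rate under the stricter rule, and m the share of that arm's stricter-rule failures that pass on the total. The SAP rate is p + m(1 − p). If m is the same in both arms, the difference becomes (1 − m) times the stricter-rule difference and so shrinks. If m differs, the difference can move either way. As a purely hypothetical case, stricter rates of 80% and 80%, with 0 and 5 percentage points of added successes, give 80% against 85%. The documents contain nothing from which m could be estimated in either arm.

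**The case against.** The strongest reply is that single-segment failures are not hidden. SAP 3.2.1.2.2 also summarises left, transverse and right scores separately, each with an ANOVA-adjusted arm difference, 95% CI and p-value, and repeats this by country. An arm difference confined to one part of the colon could be seen there. That stands against any claim that the SAP conceals segmental results. What those analyses do not give is a per-subject answer: separate segment means, quartiles and ranges do not show how many subjects had all three segments adequate at once.

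A second reply is that the BBPS responder is a variable of its own, openly based on the total. A reader might infer that it contradicts the trial's definition of success. The documents do not support that. The full-and-reliable-examination wording belongs to grades 3 and 4 of the Cleansing Score, and nothing links the two scales or requires them to agree. The BBPS rule is looser, no more.

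Third, no document sets a minimum of 2 per segment. That is correct. The minimum is a reasonable reading of Table 3, where 2 is the lowest score with the mucosa well seen; the plan does not require it.

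Finally, the endpoint is secondary and descriptive, and the primary endpoint has its own robustness analyses: the per-protocol repeat, the identity-link model and the bootstrap. This limits the importance of the point but does not repair the definition.

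**Conclusion.** The definitional gap is real and follows from the SAP alone. A colon with one segment scored 0 (with 3 and 3), or scored 1 (with 2 and 3, or 3 and 3), can be counted as a BBPS success. Twelve of the 20 passing patterns are of this kind.

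Three stronger readings are tempting and are not supported:

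- That any colon with a segment at 0 or 1 is a success. It can be, but 44 of the 56 such patterns fail.
- That 12 of 20, or 60%, of the reported successes would be false. The enumeration gives every pattern equal weight and says nothing about how often each occurs in patients.
- That the rule pulls the arms together. This needs an equal pass-through share in both arms, which the documents do not establish.

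The size in patients is therefore unknown. The conclusion assumes only that the rule is programmed as written and that Table 3 carries its plain meaning. The primary analysis, the non-inferiority decision and the sample size are untouched. It is a cheap improvement to a secondary endpoint.

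**What to change.** In SAP 3.2.1.2.2, define BBPS success as a score of 2 or more in each of the left, transverse and right colon. A separate clause for the total is unnecessary, because this already implies 6 or more. Report the plain total of 6 or more beside it as a supportive line; the gap between the two rates shows directly how many subjects passed with an inadequately seen segment. Add the BBPS success derivation to SAP Appendix 1, where it is missing.

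If treatment codes have already been opened, keep the total-score rate as the planned result and label the all-segments rate as added afterwards.

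The cost is a sentence or two in the SAP, a short derivation and an extra table row. Segment scores are already collected, so no new data are needed. The downside is that the BBPS success rate will be lower or unchanged, by an amount that cannot be stated in advance.
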